5.3.2.1 Dose Delay Criteria for Nivolumab

Dose delay criteria apply for all drug-related AEs. A treatment delay up to 4 weeks, i.e. 6 weeks calculated from the last dose, is allowed. A treatment delay beyond this must be discussed with the Study leadership. A treatment delay beyond 10 weeks is not allowed.

Tumor assessments should continue per protocol schedule, even if dosing is delayed.

Nivolumab administration should be delayed for the following reasons:

- Any Grade ≥ 2 non-skin drug-related adverse event, except for fatigue and laboratory abnormalities
- Any Grade 3 skin drug-related adverse event
- Any Grade 3 drug-related laboratory abnormality
- Any adverse event, laboratory abnormality, intercurrent illness or other reason which, in the judgment of the investigator, warrants delaying the dose of study medication.

Subjects who require delay of nivolumab should be re-evaluated weekly or more frequently if clinically indicated. Nivolumab dosing can be resumed on the established dosing schedule when retreatment criteria are met (Section 5.3.2.2).

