5.3.2.2 Criteria to Resume Dosing for Nivolumab

Subjects may resume treatment with study drug when the drug-related AE(s) resolve to Grade ≤ 1 or baseline value, with the following exceptions:

- Subjects may resume treatment in the presence of grade 2 fatigue
- Drug-related pulmonary toxicity, diarrhea or colitis must have resolved to baseline before treatment is resumed.
- Subjects with drug-related endocrinopathies adequately controlled with only physiologic hormone replacement may resume treatment.

- Subjects who received systemic corticosteroids for management of any drug-related toxicity must be off corticosteroids or have tapered down to an equivalent dose of prednisone ≤ 10 mg/day.

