5.3.2.3 Treatment Discontinuation Criteria for Nivolumab

Nivolumab treatment should be permanently discontinued for the following:

- Any grade 4 drug-related toxicity
- Any Grade 2 drug-related uveitis, eye pain or blurred vision that does not respond to topical therapy and does not improve to Grade 1 severity within the re-treatment period OR requires systemic treatment.
- Any Grade 3 non-skin, drug-related adverse event lasting > 7 days, with the following exceptions for laboratory abnormalities, drug-related uveitis, pneumonitis, bronchospasm, hypersensitivity reactions, infusion reactions, and endocrinopathies:
 - Grade 3 drug-related uveitis, pneumonitis, bronchospasm, hypersensitivity reaction, or infusion reaction of any duration requires discontinuation
 - Grade 3 drug-related endocrinopathies adequately controlled with only physiologic hormone replacement do not require discontinuation
 - Grade 3 drug-related laboratory abnormalities do not require treatment discontinuation except:
 - Grade 3 drug-related thrombocytopenia > 7 days or associated with bleeding requires discontinuation
- Any drug-related liver function test (LFT) abnormality that meets the following criteria require discontinuation:
 - AST or ALT > 5 x ULN for 2 weeks
 - AST or ALT > 5 x ULN
 - Total bilirubin > 3 x ULN
- Any Grade 4 drug-related adverse event or laboratory abnormality, except for the following events which do not require discontinuation:
 - Grade 4 neutropenia ≤ 7 days
 - Grade 4 lymphopenia or leukopenia
 - Isolated Grade 4 amylase or lipase abnormalities that is not associated with symptoms or clinical manifestations of pancreatitis. The Study leadership should be consulted for Grade 4 amylase or lipase abnormalities.
 - Isolated Grade 4 electrolyte imbalances/abnormalities that are not associated with clinical sequelae and are corrected with supplementation/appropriate management within 72 hours of their onset
 - Grade 4 drug-related endocrinopathy adverse events, such as adrenal insufficiency, ACTH deficiency, hyper- or hypothyroidism, or glucose intolerance, which resolve or are adequately controlled with physiologic hormone replacement (corticosteroids, thyroid hormones) or glucose-controlling agents, respectively, may not require discontinuation after discussion with and approval from the Study leadership.
- Any event that leads to delay in dosing lasting > 6 weeks from the previous dose requires discontinuation, with the following exceptions:

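### The dose-delay rule in 5.3.2.1 exempts fatigue at every grade, so drug-related Grade 3 fatigue of 7 days or less is held only on investigator judgment

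*Combined protocol and SAP*

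**What the plan says.** Section 5.3.2.1 gives four reasons for which nivolumab should be delayed:

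- for events outside the skin: "Any Grade ≥ 2 non-skin drug-related adverse event, except for fatigue and laboratory abnormalities"
- for the skin, in a separate bullet: "Any Grade 3 skin drug-related adverse event"
- for laboratory findings, likewise on their own: "Any Grade 3 drug-related laboratory abnormality"
- at the physician's discretion, whatever "in the judgment of the investigator, warrants delaying the dose of study medication"

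The same section adds: "Subjects who require delay of nivolumab should be re-evaluated weekly or more frequently if clinically indicated".

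Section 5.3.2.2 sets the restart level at Grade 1 or below, or baseline, with an exception for fatigue: "Subjects may resume treatment in the presence of grade 2 fatigue".

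Section 5.3.2.3 lists the permanent stops. They include "Any grade 4 drug-related toxicity" and "Any Grade 3 non-skin, drug-related adverse event lasting > 7 days". The exceptions to the second do not include fatigue. The last bullet of 5.3.2.3 adds a permanent stop when the investigator sees a substantial clinical risk in further dosing.

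Section 5.3.1 allows doses to be interrupted, delayed or discontinued as needed, and gives each infusion a window of 3 days either side. Section 5.3.2 allows a change of dose only for dose-limiting toxicity.

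**The concern.** The fatigue exemption has no upper grade. The phrase exempts two things, fatigue and laboratory abnormalities. The second is brought back at Grade 3 by a separate bullet, and skin events also have a Grade 3 bullet. Fatigue is the one category in the list with no named trigger at Grade 3.

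The restart rule points the other way. It tolerates fatigue at Grade 2, which suggests that the exemption was meant for Grade 2, but it operates only once a dose has been held. The duration rule then moves Grade 3 fatigue to permanent discontinuation after day 7, without the hold that other Grade 3 non-skin events pass through first.

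At stake are individual safety and consistent dosing. A scheduled infusion can be given in line with the listed fatigue rule while the 7-day count is running, and two physicians can handle the same patient differently without either departing from the protocol.

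**Working it through.** The plan gives no figure on this point. The check is a trace through the rules, followed by day counts.

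**1. Drug-related fatigue through each rule**

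| State | Delay (5.3.2.1) | Restart if held (5.3.2.2) | Permanent stop (5.3.2.3) |
|---|---|---|---|
| Grade 2 | exempt; judgment only | allowed | no named trigger |
| Grade 3, 7 days or less | exempt; not skin, not laboratory; judgment only | not allowed, unless baseline | only if investigator sees substantial risk |
| Grade 3, more than 7 days | exempt; judgment only | not allowed, unless baseline | yes |
| Grade 4 | exempt; judgment only | not allowed, unless baseline | yes |

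Only the second row is open: the restart rule bars dosing, yet no named rule stops it from going ahead. Section 9.8 does not close it. After a single Grade 3 event during escalation it adds a patient to the dose level, but it does not hold the affected patient's next infusion.

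**2. How many infusions can fall in the gap**

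Inputs: infusions every 14 days (5.2), window of 3 days either side (5.3.1), so intervals of 14 − 3 = 11 to 14 + 3 = 17 days. Let L be the days of continuous Grade 3 fatigue at an infusion; the gap is L = 1 to 7. Duration at the next infusion is L + interval.

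| Interval | Duration at next infusion | Still 7 days or less? |
|---|---|---|
| 11 days | 12 to 18 days | no |
| 14 days | 15 to 21 days | no |
| 17 days | 18 to 24 days | no |

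So at most one infusion per continuous episode. If that infusion is given and the fatigue persists, the 7-day limit is passed 8 − L days later, that is after 1 to 7 days.

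**3. What a hold would do**

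At the first weekly re-evaluation, hold day 7, a continuous episode has lasted L + 7 = 8 to 14 days, which is a permanent stop. Otherwise the fatigue has dropped below Grade 3 and a restart is allowed. One re-evaluation settles either case.

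**4. Effect on concurrent dosing**

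Infusions fall on Days 1, 15, 29, 43 and 57. Radiotherapy occupies Cycles 2 and 3 (5.2.1, Table 1), Days 15 to 42, so two infusions are concurrent: Days 15 and 29. Section 5.3.2.1 says that dosing picks up on the established schedule, while 5.3.1 bases later doses on the actual date of the previous one. The two readings give different results.

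| Held dose | Restart when criteria are met, after 7 days | Restart at next planned date (14 days) |
|---|---|---|
| Day 15 | Day 22, within radiotherapy | Day 29, within; one of two concurrent infusions lost |
| Day 29 | Day 36, within radiotherapy | Day 43, after radiotherapy; one of two lost |

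**The case against.** The best defence is that the case is already covered. The judgment bullet stands under the same lead-in as the other three, and all four say that dosing should be delayed. The real contrast is therefore between a named trigger and a judgment trigger, not between a mandatory rule and a loose permission. Adverse events and ECOG status are reviewed at dosing visits (7.0, 8.1.2.1.4), so the judgment is prompted. Leaving a subjective symptom to the physician is a legitimate choice, and the 7-day limit can be read as deliberately separating short from persistent Grade 3 events. The Investigator's Brochure, to which the protocol refers for adverse-event management, may say more.

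Much of this stands. An investigator can hold the dose, and the last bullet of 5.3.2.3 allows a permanent stop, though not a hold. The Brochure cannot be checked here; fatigue is not among the algorithm groups named in 5.3.2.5.

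It does not explain why fatigue alone lacks a Grade 3 trigger, or why a patient may be dosed at a grade that would bar restart. If the restart rule shows that the exemption was meant for Grade 2 only, that supports writing it into the rule that governs dosing.

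A reader might also infer that the protocol obliges physicians to dose through Grade 3 fatigue, or that 5.3.2.1 and 5.3.2.3 contradict each other. The text supports neither: a hold is always open, and the rules can all be followed at once.

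**Conclusion.** The point holds as an inconsistency in a patient-safety rule, of low weight. Drug-related Grade 3 fatigue of 7 days or less has only a judgment trigger for delay, although the restart and discontinuation rules are stricter. The exposure is at most one infusion per continuous episode.

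This assumes continuous Grade 3 fatigue, attributed to nivolumab, counted in whole days, with infusions at least 11 days apart. The documents give no frequency for Grade 3 fatigue, so no number of patients can be stated.

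A reader might infer that the gap distorts the safety results or the choice of dose. The documents do not support that. The adverse events in 6.1 and the Grade 3 events in 9.8 count whether or not the next dose is held, and nothing shows that the infusion alters the course of the fatigue. If the fatigue passes 7 days, the permanent stop follows with or without a hold.

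**What to change.** Add one bullet to 5.3.2.1, beside the Grade 3 skin and laboratory bullets: *Any Grade 3 drug-related fatigue*. Equivalently, limit the exemption in the first bullet to Grade 2 fatigue and leave its laboratory part as it is. Sections 5.3.2.2 and 5.3.2.3 need no change. The sequence is then: Grade 2, continue; Grade 3 for 7 days or less, hold and restart at Grade 2 or below (or baseline); Grade 3 for more than 7 days, permanent stop.

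The change needs a protocol version submitted to the Ethics Committee (12.3). Each newly held patient has one infusion delayed and at least one weekly re-evaluation. During radiotherapy the cost depends on how 5.3.2.1 is read. If dosing waits for the next planned date, one of the two concurrent infusions is lost; if it may restart once the criteria are met, a 7-day hold keeps the dose within radiotherapy. Concurrent administration is the subject of the primary objectives, so the amendment should also say which reading applies. The protocol already accepts this cost for every other drug-related event of Grade 2 or higher that is neither skin nor laboratory. The sample size does not change.

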5.3.2.2 Criteria to Resume Dosing for Nivolumab

Subjects may resume treatment with study drug when the drug-related AE(s) resolve to Grade ≤ 1 or baseline value, with the following exceptions:

- Subjects may resume treatment in the presence of grade 2 fatigue
- Drug-related pulmonary toxicity, diarrhea or colitis must have resolved to baseline before treatment is resumed.
- Subjects with drug-related endocrinopathies adequately controlled with only physiologic hormone replacement may resume treatment.

- Subjects who received systemic corticosteroids for management of any drug-related toxicity must be off corticosteroids or have tapered down to an equivalent dose of prednisone ≤ 10 mg/day.

5.3.2.3 Treatment Discontinuation Criteria for Nivolumab

Nivolumab treatment should be permanently discontinued for the following:

- Any grade 4 drug-related toxicity
- Any Grade 2 drug-related uveitis, eye pain or blurred vision that does not respond to topical therapy and does not improve to Grade 1 severity within the re-treatment period OR requires systemic treatment.
- Any Grade 3 non-skin, drug-related adverse event lasting > 7 days, with the following exceptions for laboratory abnormalities, drug-related uveitis, pneumonitis, bronchospasm, hypersensitivity reactions, infusion reactions, and endocrinopathies:
 - Grade 3 drug-related uveitis, pneumonitis, bronchospasm, hypersensitivity reaction, or infusion reaction of any duration requires discontinuation
 - Grade 3 drug-related endocrinopathies adequately controlled with only physiologic hormone replacement do not require discontinuation
 - Grade 3 drug-related laboratory abnormalities do not require treatment discontinuation except:
 - Grade 3 drug-related thrombocytopenia > 7 days or associated with bleeding requires discontinuation
- Any drug-related liver function test (LFT) abnormality that meets the following criteria require discontinuation:
 - AST or ALT > 5 x ULN for 2 weeks
 - AST or ALT > 5 x ULN
 - Total bilirubin > 3 x ULN
- Any Grade 4 drug-related adverse event or laboratory abnormality, except for the following events which do not require discontinuation:
 - Grade 4 neutropenia ≤ 7 days
 - Grade 4 lymphopenia or leukopenia
 - Isolated Grade 4 amylase or lipase abnormalities that is not associated with symptoms or clinical manifestations of pancreatitis. The Study leadership should be consulted for Grade 4 amylase or lipase abnormalities.
 - Isolated Grade 4 electrolyte imbalances/abnormalities that are not associated with clinical sequelae and are corrected with supplementation/appropriate management within 72 hours of their onset
 - Grade 4 drug-related endocrinopathy adverse events, such as adrenal insufficiency, ACTH deficiency, hyper- or hypothyroidism, or glucose intolerance, which resolve or are adequately controlled with physiologic hormone replacement (corticosteroids, thyroid hormones) or glucose-controlling agents, respectively, may not require discontinuation after discussion with and approval from the Study leadership.
- Any event that leads to delay in dosing lasting > 6 weeks from the previous dose requires discontinuation, with the following exceptions:
 - Dosing delays to allow for prolonged steroid tapers to manage drug-related adverse events are allowed.
 - Dosing delays lasting > 6 weeks from the previous dose that occur for non-drug-related reasons may be allowed, if approved by the Study leadership.

- Prior to re-initiating treatment in a subject with a dosing delay lasting > 6 weeks, the Study leadership must be consulted. Tumor assessments should continue as per protocol even if dosing is delayed. Periodic study visits to assess safety and laboratory studies should also continue every 6 weeks or more frequently if clinically indicated during such dosing delays.
- Any adverse event, laboratory abnormality, or intercurrent illness which, in the judgment of the Investigator, presents a substantial clinical risk to the subject with continued nivolumab dosing.

For detailed information see the IB for nivolumab.

5.3.2.4 Continuing Nivolumab with Suspected Progression

Accumulating evidence indicates that a minority of subjects treated with immunotherapy may derive clinical benefit despite initial evidence of disease progression, eg, due to inflammatory reaction simulating progression (“tumor flare” or pseudoprogression). Subjects may, at investigator discretion and agreement with the Study leadership, continue nivolumab in the setting of suspected progression until progression is confirmed. If the investigator believes that the subject continues to derive clinical benefit by continuing treatment, the subject should continue monitoring/assessments according the same schedule as patients without tumor progression, with more frequent radiologic assessment if clinically indicated (see below).

Subjects may continue nivolumab beyond initial (suspected) progression only if they meet the following criteria:

- Subject is in stable performance status (ECOG 0-1) and tolerating nivolumab
- Treatment will not delay intervention to prevent imminent complications
- Investigator-assessed overall clinical benefit

Radiographic assessment should be repeated after suspected progression as clinically required in order to determine whether there has been a decrease in the tumor size or continued progression. Potential for clinical benefit should be balanced by clinical judgment as to whether the subject is clinically deteriorating and unlikely to receive benefit from continued treatment with nivolumab. Nivolumab treatment should be discontinued permanently upon confirmation of progression.

5.3.2.5 Management Algorithms for Immuno-Oncology Agents

Immuno-oncology (I-O) agents are associated with AEs that can differ in severity and duration than AEs caused by other therapeutic classes. Nivolumab is considered an immuno-oncology agent in this protocol. Early recognition and management of AEs associated with immune oncology agents may mitigate severe toxicity. Management Algorithms have been developed to assist investigators in assessing and managing the following groups of AEs:

- Gastrointestinal
- Renal
- Pulmonary
- Hepatic
- Endocrinopathy
- Skin
- Neurological

The above algorithms are found in the nivolumab Investigator Brochure.

5.3.2.6 Treatment of Nivolumab-Related Infusion Reactions

Since nivolumab contains only human immunoglobulin protein sequences, it is unlikely to be immunogenic and induce infusion or hypersensitivity reactions. However, if such a reaction were to occur, it might manifest with fever, chills, rigors, headache, rash, pruritus, arthralgias, hypotension, hypertension, bronchospasm, or other allergic-like reactions. All Grade 3 or 4 infusion reactions should be reported within 24 hours to the study medical monitor and reported as an SAE if it meets the criteria. Infusion reactions should be graded according to NCI CTCAE (Version 4.0) guidelines.

Treatment recommendations are provided below and may be modified based on local treatment standards and guidelines, as appropriate:

For **Grade 1** symptoms: (mild reaction; infusion interruption not indicated; intervention not indicated):

- Remain at bedside and monitor subject until recovery from symptoms. The following prophylactic premedications are recommended for future infusions: diphenhydramine 50 mg (or equivalent) and/or acetaminophen/paracetamol 325 to 1000 mg at least 30 minutes before additional nivolumab administrations.

For **Grade 2** symptoms: (moderate reaction required therapy or infusion interruption but responds promptly to symptomatic treatment (eg, antihistamines, non-steroidal anti-inflammatory drugs, narcotics, corticosteroids, bronchodilators, IV fluids); prophylactic medications indicated for ≤ 24 hours):

- Stop the nivolumab infusion, begin an IV infusion of normal saline, and treat the subject with diphenhydramine 50 mg IV (or equivalent) and/or acetaminophen/paracetamol 325 to 1000 mg; remain at bedside and monitor subject until resolution of symptoms. Corticosteroid and/or bronchodilator therapy may also be administered as appropriate. If the infusion is interrupted, then restart the infusion at 50% of the original infusion rate when symptoms resolve; if no further complications ensue after 30 minutes, the rate may be increased to 100% of the original infusion rate. Monitor subject closely. If symptoms recur, then no further nivolumab will be administered at that visit.
- For future infusions, the following prophylactic premedications are recommended: diphenhydramine 50 mg (or equivalent) and/or acetaminophen/paracetamol 325 to 1000 mg should be administered at least 30 minutes before nivolumab infusions. If necessary, corticosteroids (up to 25 mg of SoluCortef or equivalent) may be used.

For **Grade 3 or 4** symptoms: (severe reaction, Grade 3: prolonged [ie, not rapidly responsive to symptomatic medication and/or brief interruption of infusion]; recurrence of symptoms following initial improvement; hospitalization indicated for other clinical sequelae (eg, renal impairment, pulmonary infiltrates). Grade 4: Life threatening; pressor or ventilatory support indicated):

- Immediately discontinue infusion of nivolumab. Begin an IV infusion of normal saline and treat the subject as follows: Recommend bronchodilators, epinephrine 0.2 to 1 mg of a 1:1000 solution for subcutaneous administration or 0.1 to 0.25 mg of a 1:10,000 solution injected slowly for IV administration, and/or diphenhydramine 50 mg IV with

methylprednisolone 100 mg IV (or equivalent), as needed. Subject should be monitored until the Investigator is comfortable that the symptoms will not recur. Nivolumab will be permanently discontinued. Investigators should follow their institutional guidelines for the treatment of anaphylaxis. Remain at bedside and monitor subject until recovery of the symptoms.

In case of late-occurring hypersensitivity symptoms (eg, appearance of a localized or generalized pruritus within 1 week after treatment), symptomatic treatment may be given (eg, oral antihistamine or corticosteroids).

5.4 Concomitant Treatments

It is expected that enrolled subjects will have systemic corticosteroids tapered as quickly as clinically appropriate during screening phase, and discontinued if possible prior to inclusion.

Supportive care for all disease-related or treatment-related adverse events should be maximized for all subjects on this study.

5.4.1 Prohibited and/or Restricted Treatments

Immunosuppressive agents, including systemic corticosteroids, are prohibited during study treatment unless utilized to treat a drug-related adverse event. Subjects with a condition requiring systemic treatment with either corticosteroids (> 20 mg daily prednisone or > 3 mg dexamethasone per day (or equivalent) or other immunosuppressive medications (including within 14 days of inclusion) are excluded. Subjects continuing to require supra-physiologic steroids (prednisone > 20 mg daily or > 3 mg dexamethasone per day or equivalent) may not be included. Inhaled or topical steroids, and adrenal replacement steroid doses \leq 20 mg daily prednisone or \leq 3 mg dexamethasone per day or equivalent, are permitted in the absence of active autoimmune disease.

